7.6 Statistical Analysis Methodology

A separate SAP will be finalized, providing detailed methods for all endpoints. In general, descriptive or summary statistics (n, mean, standard deviation, median, minimum and maximum values for continuous variables, and number [%] of subjects in each category for categorical variable) will be provided by visit. Source data for summary tables and statistical analyses will be presented as subject data listings.

All statistical analyses will be performed using SAS (version 9.3 or higher). No formal statistical analysis will be performed, as the open-label extension study is not powered for inferential statistics. Two-sided 95% confidence intervals will be provided where appropriate. No imputation will be done for missing data. The SAP will specify up to which visit summaries will be produced, as not all subjects will have been in the study for the same length of time. Further details on the analysis of efficacy endpoints will be provided in the SAP.

The study period is defined as baseline (Day 0) through end of study. Change from baseline will be between baseline (Day 0) and scheduled visits.

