3.1 Study Design

This is a multicenter, Phase 2, open-label extension study that will assess the long-term safety and tolerability of GTx-024.

The current study will enroll the following subjects from G201002:

- From the first 225 subjects enrolled in G201002, only subjects randomly assigned to the placebo group and who have completed the 12-week treatment period and 16-week durability period will be allowed to enroll in this study, once data from G201002 are unblinded. Placebo subjects who enrolled in the durability extension study (G201003) will be allowed to discontinue participation in G201003, once data from G201002 have been unblinded
- From Subject 226 onwards, any subject who was randomly assigned to any treatment group and who has completed the 12-week treatment period and the 4-week follow-up period in Study G201002

All subjects in this study will receive GTx-024 3 mg orally, once daily.

The study consists of the following visits:

Baseline (Day 0)

Subjects will be evaluated, and an additional written informed consent for the open-label extension study will be obtained. Procedures will be performed at baseline as specified in the schedule of events (Table 12–1) for the study.

Long-term Open-label Extension Period

Subjects who continue to meet the eligibility criteria will attend clinic visits at 4-week intervals for the first 12 weeks of the open-label extension study (i.e., Weeks, 4, 8, and 12). Following the first 12 weeks, subjects will attend clinic visits every 12 weeks (i.e., 12 weeks from Visit 3 onwards). At each clinic visit, study procedures will be performed as specified in the schedule of events (Table 12–1).

There is currently no planned end to this study; instead, subjects will be on treatment and followed until marketing approval is granted to GTx-024 or until the withdrawal of the Investigational New Drug application. If marketing approval is granted to GTx-024, a plan

for the transition of subjects from study drug to commercial drug product or other therapy will be implemented.

Data from this open-label extension study will be used to assess the long-term safety and tolerability of GTx-024.

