3.1.1.1 Risk Mitigation

This study has been designed to mitigate known risks associated with the use of GTx-024. Clinical study G200501 observed the effects of administering doses of 0.1, 0.3, 1, and 3 mg of GTx-024 (or placebo) for 86 days to healthy subjects: postmenopausal women and elderly men. Dose-dependent increases in serum alanine aminotransferase (ALT) and aspartate aminotransferase (AST) were observed. A higher incidence of transient, asymptomatic increases in ALT levels reported as AEs occurred in the group receiving GTx-024 3 mg (20.8%) compared with the placebo group (0%). One subject who received 3 mg/day of GTx-024 was discontinued due to an ALT level >3 times the upper limit of normal (ULN). The ALT levels returned to normal with continued exposure to GTx-024 in most cases and, furthermore, in instances when dosing was not continued, levels returned to normal. No significant increases in levels of total bilirubin, gamma glutamyl transferase, alkaline phosphatase, or lactate dehydrogenase have been observed in subjects with elevated ALT levels. Consistent with the effects of other orally administered anabolic agents, GTx-024 causes a dose-dependent reduction in high-density lipoprotein (HDL), the clinical significance of which is unknown at this time. The proposed mechanism for reduction in HDL is due to stimulation of reverse cholesterol transport and increased HDL catabolism by hepatic lipase. Reductions in HDL levels are temporary and typically return to baseline levels 12 months after treatment initiation.

In an ongoing, Phase 2 study of GTx-024 in estrogen receptor-positive/androgen receptor-positive breast cancer that is examining daily doses of GTx-024 at 9 and 18 mg, several cases of clinically significant hypercalcemia have been observed that were assessed by the investigators as possibly related to GTx-024. Subjects with hypercalcemia had

estrogen receptor–positive breast cancer with bone metastases. Hypercalcemia has not been observed in previous studies of healthy individuals or at doses <9 mg.

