4.1.1 Inclusion Criteria

Each subject must meet all of the following criteria to be enrolled in this study:

1. Be an eligible subject from G201002, where an eligible subject is defined as:
 - a. one of the first 225 subjects who were randomly assigned to the placebo group in G201002 and who have completed the required treatment and durability periods of that study, or;
 - b. any subject from 226 onwards, who was randomly assigned to any treatment group and who completed the required treatment and follow-up periods of that study
2. Be able to read, understand, and provide written, dated informed consent prior to enrollment in the current study and be likely to comply with the study protocol and communicate with study personnel about AEs and other clinically important information
3. Provide written consent to participate in the study within the following timeframes:
 - a. for G201002 Subjects 1-225, within 30 days after the unblinding of G201002 (subjects who consent to participate in G201003 will be allowed to discontinue from that study and consent to this study upon unblinding of G201002)
 - b. for G201002 Subjects 226-493, within 30 days of completing both the treatment and follow-up period of G201002

4. Agree to maintain a stable dose of any medication known to affect lower urinary tract function, including but not limited to anticholinergics, tricyclic antidepressants, beta-3 adrenergic agonists, or α -adrenergic blockers, throughout the duration of the study

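### Change is taken only from Day 0, which for women treated with GTx-024 in G201002 is a post-exposure value, so cumulative change may be understated for any effect that still persists

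*Combined protocol and SAP*

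**What the plan says.** **Reference point.** Section 7.6 states: "Change from baseline will be between baseline (Day 0) and scheduled visits". The synopsis repeats this, and Section 7.6.1 builds the laboratory shift tables on the same baseline value. Four of the five primary safety measures in Section 7.1 are changes from baseline: clinical laboratory values, SHBG and testosterone, vital signs, and endometrial thickness. So are four of the five efficacy endpoints in Section 7.2; the fifth, the PGI-I, is improvement relative to baseline. No section uses a value recorded before dosing in G201002.

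**Who enters, and when.** Among the first 225 parent subjects, only placebo women may enter. After that, Section 4.1.1 admits "any subject from 226 onwards, who was randomly assigned to any treatment group". Section 3.1 requires that such a woman has "completed the 12-week treatment period and the 4-week follow-up period in Study G201002". Consent is due "within 30 days of completing both the treatment and follow-up period of G201002", and Section 3.1 places it at the baseline visit, where "an additional written informed consent for the open-label extension study will be obtained". Section 7.5 plans no subgroup analyses, so there is no split by prior treatment.

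**Persistence of effect.** Section 3.1.1.1 says: "Reductions in HDL levels are temporary and typically return to baseline levels 12 months after treatment initiation". It also says that ALT returned to normal where dosing was not continued, without saying how quickly. Section 1.1 lists a 16-week durability period in G201002, and Section 3.1 mentions a durability extension (G201003). Neither section says what was expected of them.

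**The concern.** The primary objective is long-term safety and tolerability. For a woman already treated in G201002, the natural long-term question is how far she has moved since she first took the drug. Change from Day 0 answers a narrower one: how far she has moved since re-starting.

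The two answers agree only if nothing remains of the first course at Day 0. If something does remain, it is subtracted out of every change score and absorbed into the starting category of every shift table. The measures exposed to this include lipids, SHBG, testosterone, endometrial thickness and leak counts.

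Placebo entrants do not have this problem. With no split by prior treatment, one mean combines two kinds of baseline. Splitting the tables would separate the groups, but it would not give the previously treated women an unexposed reference.

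**Working it through.** The protocol states no figure on this point, so there is nothing to reproduce. The check has three parts.

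**1. Where Day 0 falls for previously treated women**

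Inputs: 12 weeks of treatment and 4 weeks of follow-up (Section 3.1), and consent up to 30 days later (Section 4.1.1). The calculation takes parent visits as on schedule and Day 0 as the day of consent.

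- Time off drug: 4 × 7 = 28 days, up to 28 + 30 = 58 days (4.0 to 8.3 weeks).
- Time since first dose: (12 + 4) × 7 = 112 days, up to 112 + 30 = 142 days (16.0 to 20.3 weeks).

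**2. What that does to a change score**

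For each woman this identity is exact:

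change from Day 0 = change from parent baseline − (Day 0 − parent baseline)

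The difference between the two measures is therefore the residual at Day 0. To express it as a proportion, let D be the full on-drug effect at a visit, assumed equal in both groups. Let r be the fraction of D still present at Day 0, and f the share of the pool previously treated.

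- Previously treated women show D − rD = (1 − r)D, an understatement of r.
- The pooled set shows f(1 − r)D + (1 − f)D = (1 − fr)D, an understatement of f × r.

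**3. Size in the pooled tables**

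Subjects 226 to 493 number 493 − 226 + 1 = 268. The parent allocation is not given. Let a be the proportion on active drug, the same before and after Subject 226, and assume that every eligible woman completes and enrols. Placebo women can come from all 493, so

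f = 268a / [268a + 493(1 − a)]

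| Assumed active:placebo | Previously treated | Placebo | f | f × r, r = 0 | r = 25% | r = 50% |
|---|---|---|---|---|---|---|
| 1:1 | 134 | 246 | 0.352 | 0% | 9% | 18% |
| 2:1 | 179 | 164 | 0.521 | 0% | 13% | 26% |
| 3:1 | 201 | 123 | 0.620 | 0% | 16% | 31% |

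The values of r are illustrative; the protocol supplies none.

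**Illustration on leak counts.** Section 1.1 reports a mean 81% reduction in stress episodes at 12 weeks in 18 women on 3 mg. Set the pre-treatment level to 1, so the on-drug level is 0.19, and assume the same level is reached again. With r = 50%, Day 0 is 1 − 0.81 × 0.5 = 0.595. The drop seen from Day 0 is 0.595 − 0.19 = 0.405 instead of 0.81, or 68.1% of the Day 0 level. With r = 0 the full 81% is seen.

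**The case against.** **Nothing shows that an effect remains at Day 0.** This stands, and it limits the claim. A reader might infer that drug effects are known to be built into Day 0 and that changes *are* understated. The protocol gives no half-life, no recovery time after stopping and no value at 4 weeks off drug, so only a conditional statement is supported. ALT, the leading monitored risk, is said to normalise off drug and may have recovered by Day 0.

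**The HDL sentence does not give an off-drug recovery time.** This also stands. One might read it as saying that HDL stays low until 12 months, well beyond the 16 to 20 weeks at Day 0. Its clock runs from treatment initiation, however, and it may describe resolution during continued dosing. In that case the constant-effect model in part 2 would not fit HDL, although the identity would still hold. The sentence makes a residual plausible and no more.

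**A durability period does not show durability.** Agreed. One might infer that the sponsor expected effects to outlast dosing, but the protocol only names and times these periods. Nothing connects them with laboratory, hormonal or endometrial measures.

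**Other outputs would reveal a persisting abnormality.** This holds in part. Section 7.6 provides by-visit statistics and subject listings, and Section 7.6.1 adds high and low flags, so an out-of-range laboratory value would still be flagged. AE incidence does not use a Day 0 difference. None of this recovers cumulative change, particularly for values that move within the normal range.

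**The diary may have no Day 0 value.** Section 6.1.1 hands the diary out at baseline for completion before the next visit, while Table 12-1 marks a diary at baseline. That conflict is a separate matter, but it makes the leak-count illustration less secure.

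**The SAP may deal with it.** Section 7.6 defers detailed methods to a separate SAP, which is not in the document. The SAP could add a parent-study baseline, but Section 7.6 already states the Day 0 rule and does not call for another reference.

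**Conclusion.** The concern holds in conditional form. Day 0 is the only reference for change, and for women previously on GTx-024 it is a post-exposure value taken about 28 to 58 days after the last dose. For any effect that persists to Day 0, cumulative change since first exposure may be understated by r in these women and by f × r in the pooled tables.

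The pooled figure runs from 0% to about 31%. It rests on r between 0 and 50%, a parent allocation between 1:1 and 3:1, full completion and enrolment of eligible women, and a common effect D. A range starting at 9% would presuppose that at least a quarter of the effect remains, which the protocol does not show. Nor is 31% a ceiling: a larger r, or a larger share of previously treated women, would raise it.

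Placebo entrants and recovered effects are untouched. The analysis is descriptive, so no hypothesis test is at risk; what is at risk is the completeness of the long-term safety description. Because the size is unknown and parent data could show it directly, the additional analysis is worth specifying.

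**What to change.** In Section 7.6, and in the SAP:

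1. Keep change from Day 0 as planned.
2. For women previously on GTx-024, also report change from the G201002 pre-treatment baseline. Cover laboratory values including lipids, SHBG, testosterone, vital signs, endometrial thickness, diary counts and PGI-S, wherever G201002 recorded them. The PGI-I is a comparison made by the woman herself and cannot be re-based.
3. Tabulate Day 0 minus the G201002 baseline by prior treatment. This shows any residual directly, with placebo women alongside as a guide to drift. If it is negligible, the table will say so and the Day 0 changes can be read at face value.

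The cost is linkage to the parent database and extra table columns, with no new visits or procedures. The parent baseline is also further from each visit, so change measured from it takes in more drift unrelated to the drug. That is a reason to show both references rather than replace one with the other. Which measures G201002 recorded before treatment cannot be seen from this document and should be confirmed first.

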7.6.1 Analysis of Safety Endpoints

All safety parameters (including AEs, vital signs, laboratory evaluations, SHBG, testosterone, and endometrial stripe thickness) will be summarized using the SAS set. No formal hypothesis testing will be performed.

All AEs will be coded using the latest version of MedDRA. All treatment-emergent AEs will be summarized and presented in the listings by the number of subjects who report an event, the percentage of subjects with that event, the number of events, and the grade, duration, and relationship to treatment. Percentages will be based on the number of subjects who received each treatment during the study.

Clinical laboratory safety tests will be performed, and normal ranges will be provided for each laboratory test. Values outside the normal range will be assessed for clinical significance by the investigator. Shift tables (change from baseline value to on-treatment values) will be presented for each laboratory measurement and assessment time. Each parameter outside the normal range will be designated as high (H) or low (L) in the individual data listings.

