Methods of Analysis:	
A separate statistical analysis plan (SAP) will be finalized, providing detailed methods for all endpoints. In general, descriptive or summary statistics (n, mean, standard deviation, median, minimum and maximum values for continuous variables, and number [%] of subjects in each category for categorical variable) will be provided by visit. Source data for summary tables and statistical analyses will be presented as subject data listings. No imputation for missing values will be done.
 
All statistical analyses will be performed using SAS (version 9.3 or higher). No formal statistical analysis will be performed as the open-label extension study is not powered for inferential statistics. Two-sided 95% confidence intervals will be provided where appropriate.
 
Change from baseline will be between baseline (Day 0) and scheduled visits. The SAP will specify up to which visit summaries will be produced, as not all subjects will have been in the study for the same length of time. Further details on the analysis of the efficacy endpoints will be provided in the SAP.

Safety Analyses

All safety parameters (including AEs) will be summarized using the SAS.

All AEs will be coded using the latest version of the Medical Dictionary for Regulatory Activities. All treatment-emergent AEs will be summarized and presented in the listings according to the number of subjects who report an event, the percentage of subjects with that event, the number of events, and the grade, duration, and relationship to treatment. Percentages will be based on the number of subjects who received treatment during the open-label extension study.

Efficacy Analyses

The primary analysis will be conducted on the primary endpoints at scheduled visits using the FAS.

For continuous and ordinal endpoints, the treatment effect will be summarized descriptively by visit.

List of Abbreviations

Abbreviation	Definition
AE	adverse event
ALT	alanine aminotransferase
AST	aspartate aminotransferase
CBC	complete blood count
CFR	Code of Federal Regulations
CMP	comprehensive metabolic panel
EDC	electronic data capture
eCRF	electronic case report form
FAS	full analysis set
FDA	US Food and Drug Administration
GCP	Good Clinical Practice
HDL	high-density lipoprotein
ICF	informed consent form
ICH	International Council for Harmonisation
INR	international normalized ratio
IRB	institutional review board
MedDRA	Medical Dictionary for Regulatory Activities

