7.1 Primary Safety Endpoint

The primary objective in this study is to assess the safety and tolerability of GTx-024 3 mg administered once daily in relation to the following:

- Incidence of AEs
- Change from baseline in clinical laboratory evaluations
- Change from baseline in SHBG and testosterone levels
- Change from baseline in vital sign measurements
- Change from baseline in endometrial stripe thickness as assessed with transvaginal ultrasound (only in subjects with an intact uterus)

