7.5 Description of Subgroups to be Analyzed

No subgroup analyses are planned.

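### Adverse event incidence is planned as a crude percentage of treated subjects, with no exposure-time summary, although follow-up is open-ended, staggered and unequal

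*Combined protocol and SAP*

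**What the plan says.** Section 7.1 lists "Incidence of AEs" first among five primary safety measures. The other four are changes from baseline in laboratory evaluations, in sex hormone-binding globulin and testosterone, in vital signs and in endometrial stripe thickness.

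Section 7.6.1 says that treatment-emergent AEs will be summarised by the number of subjects reporting an event, "the percentage of subjects with that event, the number of events, and the grade, duration, and relationship to treatment". The denominator is a count of people: "Percentages will be based on the number of subjects who received each treatment during the study". The synopsis (Safety Analyses) has the same kind of denominator: "Percentages will be based on the number of subjects who received treatment during the open-label extension study".

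On follow-up:
- Section 3.1 gives no planned end, and Section 4.2 says that duration is not fixed.
- Section 4.1.1 has Subjects 226-493 of G201002 consent within 30 days of completing their own treatment and follow-up periods. Placebo subjects among the first 225 consent within 30 days after G201002 is unblinded.
- Section 6.3.1.1 runs the treatment-emergent window to 30 days after drug is stopped, so the window lengthens with time on drug.

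Section 7.6 recognises the unequal follow-up: "The SAP will specify up to which visit summaries will be produced, as not all subjects will have been in the study" for equal lengths of time. It also states: "A separate SAP will be finalized, providing detailed methods for all endpoints".

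**The concern.** The stated objective is long-term safety. In a single-arm study the AE percentage is itself the result, and readers will take it as the risk on drug. A percentage of treated subjects counts a woman seen for 12 weeks and a woman seen for two years as equally observed. Two data cuts of the same cohort can then give quite different figures with no change in risk. The same figure can also arise from a steady risk or from one that rises with time on drug. The event count that Section 7.6.1 adds has no person-time beside it, so it is not a rate. The duration it mentions stands among event attributes and reads as length of the event, not of exposure.

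**Working it through.** **Plan's own figure.** There is none to reproduce. The protocol gives no AE rate, dropout rate or data cut-off, and Section 7.3 states that no power calculation was done. All rates, follow-up windows and dropout figures below are assumptions.

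**Text check.** The synopsis and Sections 7.1 to 7.6.2 contain no person-time denominator, incidence rate, time-to-onset estimate, AE summary by interval, or summary of exposure.

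**1. Dependence on follow-up.** Let *r* be the first-event rate per patient-year, constant over time, and *k* = 7/365.25 years per week. With follow-up uniform between *a* and *b* weeks:

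crude % = 100 × {1 − [exp(−*rka*) − exp(−*rkb*)] / [*rk*(*b* − *a*)]}

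For *r* = 0.10:
- 12-36 weeks (0.2300-0.6899 years): 1 − (0.97726 − 0.93333)/0.04600 = 4.5%
- 24-48 weeks (0.4600-0.9199 years): 1 − (0.95505 − 0.91211)/0.04600 = 6.7%
- 52-104 weeks (0.9966-1.9932 years): 1 − (0.90515 − 0.81929)/0.09966 = 13.8%

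Mean time at risk to first event is crude/*r* = 0.449, 0.666 and 1.385 patient-years per subject. Events divided by time at risk return 10 per 100 patient-years in all three cases.

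**2. Other rates, and dropout.** With dropout at *d* per year, the crude proportion at *w* weeks is *r*/(*r*+*d*) × {1 − exp[−(*r*+*d*)*kw*]}, averaged over the window in the same way.

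| *r* per year | *d* per year | 12-36 wk | 52-104 wk |
|---|---|---|---|
| 0.05 | 0 | 2.3% | 7.2% |
| 0.10 | 0 | 4.5% | 13.8% |
| 0.40 | 0 | 16.7% | 44.6% |
| 0.10 | 0.4 | 4.1% | 10.4% |
| 0.40 | 0.4 | 15.2% | 34.5% |

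Dropout narrows the gap but does not remove it.

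**3. Timing is lost.** Follow everyone for 104 weeks.
- Constant 0.30: 1 − exp(−0.30 × 728/365.25) = 45.0%
- 0.10 in the first 52 weeks, then 0.50: 1 − exp[−(0.10 + 0.50) × 364/365.25] = 45.0%

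The crude percentage is the same. Interval rates would read 30 and 30 per 100 patient-years in the one case, and 10 and 50 in the other.

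**4. Precision of a late interval.** Suppose 50 subjects are followed through a 52-week interval. This gives 50 × 364/365.25 = 49.8 patient-years, ignoring time lost after a first event. Five events give 10.0 per 100 patient-years (exact Poisson 95% CI 3.3-23.4).

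**5. Competing events.** Section 4.2.2 treats a subject who stops drug as withdrawn, so stopping for another reason rules out a later AE leading to discontinuation. Take 0.10 such AEs and 0.4 other stops per year, over 104 weeks (1.993 years):
- other stops treated as censoring: 1 − exp(−0.10 × 1.993) = 18.1%
- other stops treated as competing: (0.10/0.50) × [1 − exp(−0.50 × 1.993)] = 12.6%

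Any cumulative-incidence display for that outcome has to use the second form.

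**The case against.** **The SAP may deal with it.** This is the strongest reply. Section 7.6 defers detailed methods, describes only what is done in general, and plans a visit limit because time in study differs. A reader might infer from this review that the final analysis will lack exposure adjustment. The documents do not support that, because the SAP was not available. What remains is that Section 7.6.1 already fixes the AE denominator and nothing applies the visit limit to AE counting. Even if the limit did apply, a subject who left before it would still count as fully observed.

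**Summaries are by visit.** Section 7.6 and the synopsis say so in general, and number and percentage for categorical variables are included. Section 7.6.1 does not carry this over to AEs, so at best the text is unclear.

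**The study is called a 12-week extension.** The synopsis (Rationale) and Section 1.1 do so. The synopsis (Study Design), Sections 3.1, 4.2 and 6.1.3 and Table 12-1 all describe continuing follow-up, so the premise stands. These statements contradict each other and must be reconciled.

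**The contrast is constructed.** This is partly right. The widest gap comes from two windows that do not overlap. The neighbouring windows of 12-36 and 24-48 weeks differ much less, 4.5% against 6.7%. The direction does not depend on the choice of windows, but the size does.

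**All primary safety analysis ignores time.** A reader might infer this, but it is wrong. The other four measures are changes from baseline at scheduled visits, and for laboratory values, including liver enzymes, "Shift tables (change from baseline value to on-treatment values) will be presented for each laboratory measurement and assessment time".

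**Conclusion.** The point holds for AE incidence in the protocol text. The stated summary mixes event risk with length of follow-up and cannot show timing. The illustrative size is 4.5%, 6.7% or 13.8% from one assumed rate of 0.10 per patient-year, depending on the follow-up window. Those figures rest on a constant rate, uniform follow-up and, unless stated, no dropout.

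It is an optional improvement rather than an error that invalidates anything. With one arm and descriptive aims, no test, power or between-arm comparison is affected. A confidence interval around the crude percentage would not cure the problem, and rates include background events just as percentages do.

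One might also infer that AEs must be split by previous treatment in G201002. That is a separate question: Section 7.5 says "No subgroup analyses are planned", and the split is not needed to meet this point.

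**What to change.** Keep the crude number and percentage. Add to Section 7.6.1 and the synopsis, and carry into the SAP:

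- **(a)** A defined AE data cut-off and an exposure summary: total patient-years, median, range, and number at risk in each interval.
- **(b)** First-event incidence per 100 patient-years with 95% CI, by interval since first extension dose (for example 0-12, >12-24, >24-52 and >52 weeks). Time at risk runs from first extension dose to the earliest of first event, death, last contact, 30 days after last dose, or cut-off.

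If cumulative incidence is also shown for selected AEs, treat death as a competing event. For AEs leading to discontinuation, treat discontinuation for any other reason as competing too. State that censoring may be related to AE risk, since Sections 4.2.1 and 6.3.2 link withdrawal to AEs and liver findings. Reconcile the 12-week description with the open-ended design.

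**Cost.** A few extra tables. AE onset time (Section 6.3.1.3) and drug-use records (Section 5.4.2) are already collected, so study conduct does not change. The price is imprecision in late intervals, as in the 3.3-23.4 example, which the report should state.

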4.1 Selection of Study Population

Up to 500 subjects will be enrolled at around 65 sites in the United States (US). Subjects will be enrolled in the current study only if they meet all of the inclusion criteria and none of the exclusion criteria.

Deviations from the inclusion and exclusion criteria are not allowed because they can potentially jeopardize the scientific integrity of the study, regulatory acceptability, or subject safety. Therefore, adherence to the criteria as specified in the protocol is essential.

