6.2.1 Three-Day Voiding Diary

Subjects will record all urinary voids, specifying each episode of urinary leakage, including type (stress or urge). Fluid intake will also be recorded as well as any episode of vaginal discharge or spotting.

In each 3-day voiding diary, subjects are to record voiding data for 3 consecutive days in a paper diary. To be considered valid, each 3-day voiding diary must be recorded within 7 days on either side of a planned visit.

Three-day voiding diaries are reliable measures of the mean number of urinary incontinence episodes per day, incontinence type, mean number of voids per 24 hours, and mean number of voids during sleeping hours.

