6.3.3.4 Transvaginal Ultrasound

Only for subjects with an intact uterus, transvaginal ultrasound will be performed at the baseline visit, Week 12 and every 24 weeks only (i.e., every other clinic visit) to observe changes in the endometrial stripe thickness (mm). Transvaginal ultrasound examinations will be evaluated locally.

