7.4 Analysis Sets

Data analysis will be performed on a safety analysis set (SAS) and a full analysis set (FAS).

The SAS set contains all subjects in the study who receive ≥ 1 dose of study drug. All safety analyses will use the SAS.

The FAS is used for efficacy analysis. The FAS consists of all randomized subjects who receive ≥ 1 dose of study drug and have ≥ 1 postbaseline primary efficacy assessment (3-day voiding diary). Further details will be provided in the SAP.

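### The all-treated denominator understates the incidence of adverse events that can occur only in women with a uterus

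*Combined protocol and SAP*

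**What the plan says.** The AE percentage rule appears twice in the protocol. Section 7.6.1 states: "Percentages will be based on the number of subjects who received each treatment during the study". The synopsis (Methods of Analysis, Safety Analyses) states: "Percentages will be based on the number of subjects who received treatment during the open-label extension study". There is one treatment, so both mean everyone treated. Section 7.4 defines the safety analysis set as everyone with at least one dose and adds: "All safety analyses will use the SAS". Neither place makes an exception for events tied to an organ that some women lack.

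The ultrasound is handled differently. Section 6.3.3.4 begins: "Only for subjects with an intact uterus, transvaginal ultrasound will be performed at the baseline visit". Section 7.1 lists change in endometrial stripe thickness among its five primary safety measures, again only for women with an intact uterus. Nothing in the eligibility criteria (sections 4.1.1 and 4.1.2) excludes women who have had a hysterectomy.

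Section 7.5 rules out another route to an intact-uterus rate: "No subgroup analyses are planned". Section 7.6 leaves detailed methods to a separate SAP, whose text is not in the document reviewed.

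**The concern.** A woman without a uterus cannot develop endometrial thickening, endometrial hyperplasia or a uterine polyp. Under the stated rule she still counts in the denominator for those terms, so their reported incidence is too low whenever any such women are treated. There is no comparator arm in which the dilution might cancel. The reported percentage is itself the result.

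The protocol also links the scan to the AE table. Section 6.3.3 lists transvaginal ultrasound as a safety assessment, and section 6.6 has clinically significant abnormal safety assessments recorded as AEs. A significant scan finding would therefore be reported as a percentage of a group that includes women who were never to be scanned. The scan summary and the AE table would describe the same organ on two different populations, both under the primary safety objective.

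**Working it through.** The plan states no AE rate, power or sample-size figure on this point, so there is none of its own to reproduce. The check is direct arithmetic.

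**Inputs**
- N = 500 treated women, the enrolment cap in section 4.1. The actual number may be lower.
- h = share of treated women without a uterus. Not given; assumed to be 10% to 50%.
- x = number of women with a given uterus-dependent AE. Illustrative values: 5 and 0.

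**Formulas**
- Reported rate = x / N.
- At-risk rate = x / (N(1 − h)).
- Reported ÷ at-risk = 1 − h, so at-risk ÷ reported = 1 / (1 − h). This ratio does not depend on N or x.
- Intervals are exact (Clopper-Pearson), two-sided 95%, because section 7.6 mentions only two-sided 95% intervals. With zero events the upper limit is 1 − 0.025^(1/n), where n is the denominator used.

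**Results for N = 500**

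| h (assumed) | Women at risk | 1/(1 − h) | 5 affected women: rate (95% CI) | 0 affected: upper 95% limit |
|---|---|---|---|---|
| Stated rule (all 500) | – | 1.00 | 1.00% (0.33 to 2.32) | 0.74% |
| 10% | 450 | 1.11 | 1.11% (0.36 to 2.57) | 0.82% |
| 20% | 400 | 1.25 | 1.25% (0.41 to 2.89) | 0.92% |
| 30% | 350 | 1.43 | 1.43% (0.47 to 3.30) | 1.05% |
| 40% | 300 | 1.67 | 1.67% (0.54 to 3.85) | 1.22% |
| 50% | 250 | 2.00 | 2.00% (0.65 to 4.61) | 1.46% |

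Two zero-event entries worked out: 1 − 0.025^(1/500) = 0.74%, and 1 − 0.025^(1/250) = 1.46%.

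With 300 treated women instead of 500 the ratios are unchanged. The zero-event upper limit is then 1.22% under the stated rule, against 1.36% (h = 10%) to 2.43% (h = 50%) among women at risk.

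**Direction and size.** For any h above zero the reported rate is too low, by a relative 10% to 50% over the assumed range. The direction follows from the rule alone. The size depends on h, which the documents do not supply.

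**The case against.** The strongest reply is that little is lost. The AE tables give the number of women with each event, and subject listings are planned. Section 7.6 requires n for continuous variables by visit, so the baseline ultrasound n would approximate the number of women with a uterus, apart from missed scans. A reader could divide one by the other. That is true, but the reader must then rebuild the rate from an approximate denominator, because the plan does not say that the number of women with a uterus will be tabulated.

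A second reply is that the separate SAP may set an at-risk denominator. It may. But the protocol states its rule without exception, and a SAP that follows it would carry the dilution forward.

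A third reply is that the consequence is small: one treatment, no hypothesis test, and no halting rule in section 6.3.2 that uses a uterine AE rate. This stands and limits the weight of the point.

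A reader might also infer more than the documents support:
- *That the plan names the endometrium as a leading risk.* It makes stripe thickness a primary safety measure, but Risk Mitigation (section 3.1.1.1) discusses liver enzymes, HDL and calcium, not the endometrium.
- *That the primary endometrial measure is diluted.* It is not. Stripe thickness is measured only in women with a uterus.
- *That misleading confidence limits are certain to be reported.* Section 7.6 provides intervals only where appropriate and does not commit to them for individual AE terms.
- *That all gynaecological bleeding or discharge is affected.* Section 6.2.1 says of the diary: "Fluid intake will also be recorded as well as any episode of vaginal discharge or spotting". Spotting and discharge do not require a uterus, so this text is not evidence of the dilution.

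**Conclusion.** The point holds for AEs that can occur only in a woman with a uterus. Their reported incidence equals the at-risk incidence times (1 − h). The conclusion rests on two things: that some treated women lack a uterus, which the eligibility criteria allow and the ultrasound restriction implies, and that the all-treated rule is applied as written. Confidence is high for the direction. It does not extend to the size: the factor of 1.11 to 2.00 is a range over an assumed h, not an estimate from the documents. The effect on confidence limits arises only if intervals are produced for these terms.

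This is a correction to reporting and worth making, but of modest weight. It changes a few AE percentages in a descriptive study and leaves the stripe-thickness analysis and all other AE percentages as they are.

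**What to change.** In section 7.6.1 and the matching synopsis paragraph, add that for a pre-listed set of strictly uterus-dependent MedDRA terms, percentages and any confidence intervals are based on treated women with an intact uterus at Day 0. All other AEs keep the all-treated denominator. Tabulate the number of treated women with an intact uterus and footnote the denominator in the AE tables. The all-treated percentage may be kept alongside.

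Fix the term list before the data are summarised, so that the denominator is not chosen after the events are seen. Terms such as vaginal bleeding, spotting or discharge, which do not require a uterus, should be left off the list or shown on both denominators.

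The cost is one added sentence in each of the two places, a term list that needs some clinical judgement at its edges, and a footnote. No new data are needed, because uterus status already decides who is scanned at baseline (section 6.1.1). The downside is a little more table work and higher reported rates for these terms, by the factor 1/(1 − h).
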